12.2 CLINICAL LABORATORY PARAMETERS

Descriptive statistics for clinical laboratory values (in SI units) and changes from the baseline values at each assessment time point will be presented by treatment group for the following laboratory parameters:

| Hematology: | red blood cells (RBC); RBC indices: mean corpuscular volume, mean corpuscular hemoglobin, and mean corpuscular hemoglobin concentration, RBC morphology; white blood cells (WBC); WBC differential (% and absolute): neutrophils, lymphocytes, monocytes, eosinophils, basophils, hematocrit, hemoglobin, and platelets |
|-------------|---|
| Chemistry: | albumin, alkaline phosphatase, alanine aminotransferase, aspartate aminotransferase, total and direct bilirubin, blood urea nitrogen, calcium, chloride, creatinine, gamma glutamyltransferase, globulin, nonfasting glucose, potassium, total protein, and sodium |
| Urinalysis: | color, appearance of urine, specific gravity, pH, protein, glucose, ketones, occult blood, leukocyte esterase, nitrite, bilirubin, urobilinogen, crystals; microscopic examination if positive for protein, leukocyte, occult blood, nitrite, or crystals |

Shift tables from baseline to end of study for clinical laboratory parameters will be presented by treatment group for the following categories: low, normal, and high, which are provided by lab vendor.

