5.6 Treatment Regimen and Dosing

5.6.1 Treatment 1

Eligible patients will be randomized on Randomization/Day 0 to receive Treatment 1, LiRIS 400 mg/LiRIS 400 mg; LiRIS Placebo/LiRIS Placebo or LiRIS Placebo/LiRIS 400 mg (Section 5.4). Patients will have the Treatment 1, 1st IP inserted on Randomization/Day 0 and removed on Day 14. On the same day, following the 1st IP removal, the 2nd IP (LiRIS 400 mg or LiRIS Placebo) will be inserted and subsequently removed on Day 28. Patients will be followed for 20 weeks post IP removal for additional safety and efficacy assessments. In the event that a patient does not receive Treatment 2, they will exit the study at Treatment 1 Week 20 Follow-up Visit.

5.6.2 Treatment 2

All patients will receive LiRIS 400 mg for their second treatment. Patients may request, qualify, and receive Treatment 2 IP from Week 4 Follow-up until Week 20 of Treatment 1. In the event that the Treatment 2 IP cannot be inserted on the day of qualification, Treatment 2 may be rescheduled within 14 days of qualification. The LiRIS will be inserted on Treatment 2/Day 0, and will be removed on Day 14. Patients will be followed for 4 weeks post-removal and will be exited from the study.

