12.0 SAFETY ANALYSES

The safety analysis will be performed using the Safety Population. The safety parameters will include adverse events (AEs) and clinical laboratory and vital signs parameters, physical and pelvic assessments. For each clinical laboratory and vital sign parameters, the last non-missing safety assessment before the first Treatment 1 IP insertion will be used as the baseline for all analyses of that safety parameter. Continuous variables will be summarized by number of patients and mean, SD, median, minimum, and maximum values. Categorical variables will be summarized by number of patients.

All safety analyses will be performed using the safety population. For such analyses, subjects will be analyzed according to actual treatment received at the study treatment visit (i.e., "as treated" rather than "as randomized").

The following safety analyses will be performed unless otherwise mentioned:

- Summaries by treatment group and overall for the Treatment 1 period
- Summaries for patients who participated in both the Treatment 1 period and Treatment 2 period by treatment group and overall patient population. In this analysis, the treatment groups will be the safety treatment groups.

12.1 **ADVERSE EVENTS**

Adverse events will be coded by system organ class and preferred term using the *Medical Dictionary for Regulatory Activities*, version 18.1 or newer.

An AE will be considered a treatment-emergent adverse event (TEAE) if it was present after the first dose of study treatment or was present before the date of the first dose of study treatment and increased in severity after the first dose of study treatment or became serious after the first dose of study treatment. If more than 1 AE was reported before the first dose of study treatment and coded to the same preferred term, the AE with the greatest severity will be used for comparison with the AEs occurring during the study period.

Analysis of the incidence of TEAEs will be performed for the Treatment 1 Period using the Safety population. For the cohort of safety patients that received Treatment 2 IP, the incidence of TEAEs will be summarized over the Treatment 2 Period and over the entire study period (Treatment 1 and 2 period). The following rules will be used to count TEAEs at each treatment period.

- For the analyses of TEAEs by treatment period, an event will be counted once in the particular period if the onset of this event begins during that corresponding period.

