The table below presents the preferred terms identified to be of special interest for lidocaine treatment. Since lidocaine has a short half-life, for these AEs to be considered of special interest for lidocaine treatment and to be further summarized in a table they need to occur on or after the day of IP insertion and up to the day after the IP removal. For Treatment 1 period it will be up to the day after the 2nd IP removal while for Treatment 2 it will be the day after the IP removal. The summary table will present such events by treatment group and overall. This table will be updated prior to database lock for consistency with the MedDRA version (version presented below is 18.1) that will be used for the analysis.

MedDRA v18.1 PT for AEs associated with of lidocaine toxicity

MedDRA Preferred term Dizziness

- Somnolence Nervousness Feeling cold Feeling hot Confusional state Cardiac arrest Circulatory collapse Seizure Vision blurred Diplopia Hypoaesthesia Paraesthesia oral
- Hypoaesthesia oral Hypotension Bradycardia Respiratory arrest Respiratory depression Tinnitus Tremor Muscle twitching Loss of consciousness Vomiting

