17.0 DATA HANDLING CONVENTIONS

17.1 **VISIT TIME WINDOWS**

Table 17.1–1 presents, for both treatments periods, the derived visits for efficacy (excluding efficacy based on daily pain diary) and safety analyses and the corresponding range of study days (window) during which an actual visit may occur.

Following SDTM and ADaM standard, the date of first IP insertion will be considered as Treatment 1 Day 1. Similarly, the date of 2nd IP insertion will be considered Treatment 2 Day 1. However, in the assessment tables of the protocol and in Section 4 of this document and in the eCRF pages this is considered to be Treatment 1 Day 0 and Treatment 2 Day 0, respectively. For by visit analysis tables and listings the visit label will follow these protocol and eCRF visit definitions (3rd column in table 17.1-1). Some listing will also display study day using the SDTM definition. Hence, using SDTM and ADaM standards study day is calculated as follows (see 2nd column in Table 17.1-1):

Screening & baseline period (prior to IP insertion)

study day = visit date - 1st IP insertion date

Treatment 1 period :

study day = visit date - 1st IP insertion date +1

Treatment 2 Period :

study day = visit date - 2st IP insertion date +1

Throughout this document ,unless otherwise stated, this definition of study day is used.

27MAR2018 CSR 201025-001

If not stated otherwise, all by visit analysis will be using the visit windows specified above. The target day for each treatment period is referenced to days after first IP insertion within each treatment period. Treatment 1 Day 1 refers to the first IP insertion date while Treatment 2 Day 1 refers to the IP insertion date in Treatment 2 period. In contrast, if the assessment date is before date of Treatment 1 IP insertion, the study day is calculated as follows:

assessment date - date of Treatment 1 IP insertion.

The visit window for each treatment period is defined as follows:

[(target day of current visit + target day of previous visit)/2+1] to [(target day of current visit + target day of next visit)/2]

If a patient has 2 or more visits within the same visit window, the last visit with a nonmissing value will be used for the analysis.

For laboratory and vital signs analysis, baseline refers to study baseline, i.e. the baseline information collected at the start of Study 201025-001.

17.2 **DERIVED VARIABLES**

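### The only planned laboratory shift table ends at study exit, so out-of-range shifts that arise and resolve during the 28-day randomised treatment are not counted

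*SAP*

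**What the plan says.** SAP 12.2 plans two laboratory outputs. The first is descriptive: values and "changes from the baseline values at each assessment time point will be presented by treatment group". SAP 12.0 specifies that descriptive summaries include the minimum and maximum. The second is categorical, using the laboratory vendor's low, normal and high ranges: "Shift tables from baseline to end of study for clinical laboratory parameters will be presented by treatment group". The SAP text gives no shift to an on-treatment visit, to the worst post-baseline value or to the end of Treatment 1. It does not define end of study for laboratory data.

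SAP 17.1 fixes the reference point: "For laboratory and vital signs analysis, baseline refers to study baseline". The same baseline therefore serves both treatment periods.

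SAP 12.0 sets a default for safety outputs, which applies unless something else is mentioned: "Summaries by treatment group and overall for the Treatment 1 period", plus summaries for patients who took part in both periods. Grouping is as treated: "subjects will be analyzed according to actual treatment received at the study treatment visit".

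On timing, Protocol 5.6.1 says of patients who do not receive Treatment 2 that "they will exit the study at Treatment 1 Week 20 Follow-up Visit". Protocol 5.6.2 says "All patients will receive LiRIS 400 mg for their second treatment" and has those patients leave the study 4 weeks after that device is removed. Protocol 7.3.3 lists laboratory shifts from baseline without tying them to study exit. It calls for Treatment 1 summaries by group, Treatment 2 summaries, and summaries of patients in both periods.

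**The concern.** A shift table shows how many patients moved out of range, and from which starting category. If its only post-baseline point is study exit, it describes patients well after the device has gone. A value that leaves the normal range while a device is in place and returns by exit is tabulated as no change.

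The endpoint also mixes patients. Some exit without retreatment, and others exit after a further 14 days of active LiRIS. If the table is produced by Treatment 1 group exactly as worded, a placebo patient's exit value may follow active drug, which blurs the safety comparison.

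At stake is how clearly laboratory safety is described. The primary efficacy result, the sample size and the power are unaffected.

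**Working it through.** **Inputs.** Protocol 3: screening up to 4 weeks, randomised treatment 4 weeks, Treatment 1 follow-up 20 weeks, and 19 patients planned for two placebo devices. Protocol 5.6.2: Treatment 2 available from Week 4 to Week 20 Follow-up, insertion may be delayed by up to 14 days (2 weeks), device in place 14 days (2 weeks), then 4 weeks of follow-up.

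**1. The plan's own durations.**
- Treatment 1 only: 4 + 4 + 20 = 28 weeks, as stated.
- Maximum with Treatment 2: 4 + 4 + 20 + 2 (delay) + 2 + 4 = 36 weeks, as stated (34 without the delay).
- Minimum with Treatment 2: s + 4 + 4 + 2 + 4 = s + 14 weeks, where s is screening. The stated 16 needs s = 2, which is an assumption that matches the 14-day pain run-in in Protocol 6.5.12. The range is 14 (s = 0) to 18 (s = 4).

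**2. Where study exit falls for completers.**

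| | Weeks from last device removal | Weeks from last Treatment 1 removal |
|---|---|---|
| Treatment 1 only | 20 | 20 |
| Retreated, earliest | 4 | 4 + 2 + 4 = 10 |
| Retreated, latest | 4 | 20 + 2 + 2 + 4 = 28 |

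In the retreated rows, 2 weeks of active LiRIS lie inside the last column. Patients who leave early have their exit assessments when they leave (Protocol 8.7), so their interval can be shorter, down to zero.

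**3. What the table counts.** Take a patient who is normal at baseline, high at Day 14, and normal at Day 28 and at exit. The planned table records normal to normal. A table to the highest value within Treatment 1 would record normal to high.

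**4. Two readings of SAP 12.0 with 12.2.**
- *Literal:* the endpoint is study exit for everyone. Retreated patients are then compared with study baseline after active LiRIS, whatever they received in Treatment 1.
- *Default applied:* the table stops at the end of Treatment 1, which SAP 17.2 places at Treatment 2 insertion. Mixing with open-label drug disappears. Treatment 1-only completers are still assessed at 20 weeks, and a single end-of-period value still misses what arose and resolved earlier.

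The gap in step 3 remains on both readings. Mixing follows only from the first.

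**5. Size of the mixing on the literal reading.** If a proportion r of the placebo/placebo group is retreated, the share of its completers' exit values that follow LiRIS is r, or 19 × r patients. The documents give no r. Assumed values: r = 0 gives 0; r = 0.25 gives 4.75; r = 0.5 gives 9.5; r = 1 gives 19. This is a share of values. It equals the share of shifts only if retreated and other patients shift at the same rate.

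**6. Comparison with neighbouring sections.** SAP 12.3 summarises vital signs at each visit, at the end of each treatment phase and at the end of the study. SAP 12.1 counts adverse events by treatment period. The laboratory shift table has no such split. SAP 18.0 does not list the restriction to study exit as a change from the protocol.

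**7. Primary analysis.** SAP 4.0 plans the same outputs when the last patient reaches Week 4 Follow-up. A Treatment 1-only patient whose second removal came fewer than 20 − 4 = 16 weeks before the last patient's would not yet have reached Week 20 Follow-up. SAP 12.2 gives no rule for patients still in the study.

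**The case against.** The case on the other side is substantial, and most of it limits how far the point can be taken.

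- **A reader might infer that on-treatment laboratory abnormalities are invisible.** They are not. By-visit tables carry the minimum and maximum, so the most extreme value in each group at each visit is shown. Protocol 9.1.1 lets an abnormal laboratory finding be an adverse event, and 9.1.2 requires clinically relevant urine findings to be recorded as such. What is missing is narrower: how many patients crossed a limit, and from which baseline category. Adverse event reporting also depends on the investigator's judgement.
- **A reader might infer that post-LiRIS shifts will be charged to placebo.** The documents do not establish this. The SAP 12.0 default and the period split in Protocol 7.3.3 may both be meant to prevent it. The fair statement is that 12.2 does not say which rule governs.
- **A reader might take "Since lidocaine has a short half-life" in SAP 12.1 as saying that all drug effects end a day after removal.** That sentence only sets the window for a list of adverse event terms. It makes no claim about laboratory values or device effects.
- **A reader might say that every exit value is at least 4 weeks after removal, by randomised arm.** The interval holds for completers but not for early exits, and safety groups are as treated.
- **The benefit may be partial.** The visible text confirms urinalysis at all clinic visits, but the blood schedule is in Protocol Table 1, which is not shown. Without on-treatment blood samples, a worst-value table cannot recover on-treatment blood abnormalities. SAP 4.0 also places table specifications in a separate document.
- **Worst-value shifts are one convention among several.** The Amendment 2 summary records that the sponsor dropped the analysis of clinically significant laboratory abnormalities as not relevant. That choice does not explain why the retained shift table should look only at exit.

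**Conclusion.** The concern holds in a limited form. The only planned categorical laboratory output ends at study exit, which for completers is 20 weeks after the second removal or 4 weeks after removal of an active Treatment 2 device. Shifts that arise and resolve within the 28 randomised days are not counted on either reading of the SAP, though some may be seen in by-visit extremes or adverse event tables.

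Mixing with open-label LiRIS is a possible consequence of unclear wording. Its extent could be anywhere from none to all of the placebo group's completers, because no retreatment rate is given.

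This is a cheap improvement to safety reporting. The timing conclusion rests on the scheduled exits in Protocol 5.6. The gain for haematology and chemistry further depends on blood being sampled on treatment.

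**What to change.** In SAP 12.2, replace the single shift with a shift from study baseline to the worst post-baseline value (lowest and highest separately) within Treatment 1. End that window before Treatment 2 insertion and tabulate by as-treated Treatment 1 group. Add a separate shift table for Treatment 2, in line with the period separation in Protocol 7.3.3. If an exit shift is kept, define end of study for laboratory data, and say how patients still in the study at the primary analysis are handled.

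The cost is SAP wording and one or two more tables from data already being collected. The small downside is that worst-value tables show more isolated abnormal values, some of which will be chance findings. Before finalising, check Protocol Table 1 for on-treatment blood draws, so that the haematology and chemistry tables are not described as on-treatment if no such samples exist.

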12.3 VITAL SIGNS

Descriptive statistics for vital signs (systolic and diastolic blood pressures, respiratory rate, pulse rate, body temperature) and changes from baseline values at each visit and at the end of each treatment phase and study will be presented by treatment group.

12.4 ELECTROCARDIOGRAM

Not Applicable.

12.5 **OTHER SAFETY PARAMETERS**

12.5.1 Bladder Post-Void Residual

Post-void residual (PVR) volume measurement and change from baseline volume measurements will be summarized by treatment phase for each visit (for visits where PVR assessment is done) using descriptive statistics.

12.5.2 **Physical Examination**

Complete Physical examinations are performed at the baseline and at the end of each treatment phase. Abnormal findings at these visits will be summarized by treatment phase. The complete and abbreviated physical examinations results will be presented in a patient listing

12.5.3 Cystoscopic Exam

All patients will undergo a cystoscopic examination on the days of insertion and removal of the IP, Treatment 1 Week 4 Follow-up and at study exit if the patient does not continue into Treatment 2 period. Abnormal findings will be summarized by treatment phase.

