Randomization/Stratification: Randomization will be centralized and stratified by baseline pain score (≤ 5 or > 5) collected during the Screening period. Each patient within a stratum will be randomized to one of 3 groups (2 consecutive LiRIS 400 mg or 2 consecutive LiRIS Placebo or one LiRIS Placebo followed by one LiRIS 400 mg) in a 2:1:1 ratio that will define the patient's assignment in Treatment 1.

Visit Schedule:

Treatment 1:

Patients will be evaluated during the Screening period for eligibility.

Eligible patients will be:

Study Population Characteristics

[figure not shown]
Number of Patients: Approximately 76 patients will be enrolled into the study to ensure 72 evaluable patients overall for Treatment 1, including 36 patients in the LiRIS 400 mg/LiRIS 400 mg group, 18 patients in the LiRIS Placebo/LiRIS Placebo group, and 18 patients in the LiRIS Placebo/LiRIS 400 mg group.

[figure not shown]
Condition/Disease: Female patients with IC with HL

Key Inclusion Criteria:

- females \geq 18 years of age
- a diagnosis of IC with HL defined as:
 - an unpleasant sensation (pain, pressure, discomfort) perceived to be related to the urinary bladder, associated with lower urinary tract symptoms (LUTS) of more than 6 months duration in the absence of infection or other identifiable causes (van de Merwe et al, 2008), documented history or patient reported
 - and
 - documented history of an observation of HL via cystoscopic procedure in which a lesion is defined as a circumscript, reddened mucosal area that can be small vessels radiating towards a central scar, and/or a fibrin deposit of coagulum attached to this area. Lesions may also be linear, fissure-like, and may be bleeding.

Key Exclusion Criteria:

•	
_	
-	

See Section 4.4 for detailed exclusion criteria.

Response Measures

Efficacy:

Primary:

• average daily bladder pain score patient experienced over the previous 24-hour period as measured by an NRS of 0 to 10, recorded on a 7-day pain assessment tool

The primary timepoint is Week 4 following Treatment 1 2nd IP removal.

Secondary:

- number of HLs assessed by the Principal Investigator (PI) during cystoscopy
- composite score of HL calculated based on number, size, and severity of the lesions

_	
-	
_	
-	
-	
_	
_	

Safety:

- adverse events and serious adverse events
- physical examination
- vital signs
- any abnormal cystoscopy findings at insertion and removal

- pregnancy testing for women of childbearing potential

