6.5.8 Cystoscopic Examination

All patients will undergo a cystoscopic examination on the days of Insertion of the IP to rule out the presence of any bladder or urethra anatomical feature that, in the opinion of the investigator, might prevent the safe placement, indwelling use, or removal of IP, such as bladder fistulae or stone. In addition, prior to the intial IP insertion on Day 0, the presence of HLs will be confirmed. If during the cystoscopic exam, the investigator discovers an abnormality that would prevent the safe placement, indwelling use, or removal of the IP, the patient will not receive treatment and will be withdrawn from the study.

A brief cystoscopic examination for safety purposes will also be conducted on all patients at the Treatment 1 and Treatment 2 Day of Removal Visits (see Table 1).

During each cystoscopy, the investigator will count the number of lesions visible while performing the bladder scan for bladder mapping.

Investigators may recommend that the patient take pain medication up to 6 hours prior to the cystoscopic procedure and continuing for 24 hours after the procedure to minimize patient anxiety and discomfort.

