The data derivations and definitions listed in this section are to be applied to all analyses described in this analysis plan, unless otherwise stated.

- In this study there are two treatment periods:
 - Treatment period 1: for patients that just receive treatment in the randomized and blinded phase of the trial, it covers the period from the first Treatment 1 IP insertion to study exit. In contrast, for patients that receive IP insertions in both the randomized phase of the study (Treatment 1) and the open label phase of the study (Treatment 2) it covers the period from first Treatment 1 IP insertion up to Treatment 2 IP insertion,
 - Treatment period 2: covers the period from Treatment 2 IP insertion to study exit.
- Study days for each treatment period X (X=1 or 2) will be calculated as:
 - Study day of Treatment X = visit date (day 1 of Treatment X) + 1.
- The baseline value of an assessment will be the last value recorded prior to the patient being inserted with first Treatment 1 IP on Day 1.
- Unless otherwise stated no imputation will be performed for missing data. All analyses will be based on the observed data.
- For analyses that are by stratification factor, actual stratification levels rather than randomization stratification levels will be used.
- Data will be pooled across the investigational sites.
- Descriptive statistics for continuous/ordinal data include the sample size (N), mean, standard deviation (SD), median, minimum (Min), and maximum (Max) and 95% confidence intervals.
- Summary statistics for categorical variables include sample size (N), frequency count (n), and percentage (%).

17.2.1 **Pain Data Derivations**

A pain assessment tool will be utilized in the study to capture the average daily pain and the daily worst pain scores on an electronic hand held device. Patients will be asked to rate their daily pain on a pain NRS consisting of an 11 point integer scale ranging from 0 for "no pain" to 10 for "worst pain imaginable". The pain assessment will continue every day up to and including the day prior to the Exit visit.

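### SAP 12.5.3 summarises abnormal cystoscopy findings by treatment phase without reference to the Day 0 pre-insertion exam, so that safety table cannot separate new non-lesion findings from pre-existing ones

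*SAP*

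**What the plan says.** SAP 12.5.3 lists the exams: "All patients will undergo a cystoscopic examination on the days of insertion and removal of the IP", then Treatment 1 Week 4 Follow-up, and study exit for patients who do not go on to Treatment 2. Its whole analysis is "Abnormal findings will be summarized by treatment phase". It mentions no change, shift or new-finding category.

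The Protocol Summary (Response Measures, Safety) makes "any abnormal cystoscopy findings at insertion and removal" a safety measure. Protocol 6.5.8 adds that "prior to the intial IP insertion on Day 0, the presence of HLs will be confirmed", and describes the exam at removal visits as a brief one for safety. Protocol 7.3.3, which lists the safety analyses, does not name cystoscopy, so SAP 12.5.3 is the only stated safety analysis of these exams.

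Other SAP sections do refer back to baseline. For post-void residual (12.5.1), "change from baseline volume measurements will be summarized by treatment phase for each visit". Laboratory results (12.2) get shift tables from baseline. Lesion counts and bladder video (11.2) are assessed as change from baseline, but as efficacy.

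**The concern.** Cystoscopy is the direct look at the bladder wall in a trial of an indwelling device. The safety question for each patient is whether the bladder shows something after insertion that was not there before. These patients have bladder disease at entry, so some abnormal findings may precede any exposure. A tally by phase mixes those with findings that appear later.

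The usual remedy, comparison with control, is not available for a device effect. Protocol 5.1 states that active and placebo systems share the same silicone and nitinol construction, so no arm is free of the device. The within-patient comparison with Day 0 is the only reference in the trial that precedes every study device, and 12.5.3 does not call for it.

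**Working it through.** The plan gives no figure for cystoscopic findings, so there is none to reproduce, and the sample-size calculation has no bearing here. The check is mainly a reading of the text.

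**1. Is a baseline supplied elsewhere?** SAP 12.0 fixes a safety baseline, but its sentence begins "For each clinical laboratory and vital sign parameters, the last non-missing safety assessment before the first Treatment 1 IP insertion" and covers only those two data types. SAP 17.2 is general: "The baseline value of an assessment will be the last value recorded prior to the patient being inserted with first Treatment 1 IP". That would make the Day 0 exam the baseline for cystoscopy. It defines a baseline but orders no comparison with it, and 12.5.3 requests none.

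**2. Which phase holds the Day 0 exam?** For a patient without Treatment 2, SAP 17.2 says of Treatment 1 that "it covers the period from the first Treatment 1 IP insertion to study exit". The pre-insertion exam falls on that same date. Read strictly it comes before the period starts; assigned by date it falls inside. Section 12.5.3 does not say which applies.

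**3. Would a split into insertion and removal exams be enough?** No. Under Protocol 5.6.1 the first device is removed and the second inserted on Day 14, so that insertion-day exam follows 14 days of device exposure. Under Protocol 3, Treatment 2 may be inserted at the Week 4 Follow-up visit, so one exam can close Treatment 1 and precede Treatment 2. Findings have to be tied to visits and to a named reference exam.

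**4. Is a persisting finding counted twice?** SAP 12.1 prevents an unchanged adverse event from Treatment 1 being counted again in Treatment 2. Section 12.5.3 has no such rule, so a persisting finding could appear under both phases.

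**5. What does a phase tally reveal?** Suppose that a patient counts once if any exam in the phase is abnormal, and that pre-existing findings are counted, either because Day 0 is included or because they are still visible later. Let q be the share with a pre-existing countable finding and r the rate of new findings among the rest. The table shows

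P = q + (1 − q) × r.

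All values of q and r below are assumptions; none comes from the documents.

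| q | P if r = 5% | P if r = 20% |
|---|---|---|
| 30% | 33.5% | 44.0% |
| 50% | 52.5% | 60.0% |
| 70% | 71.5% | 76.0% |
| 90% | 90.5% | 92.0% |

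Read in reverse, the difficulty is one of identification. A reported 60% fits q = 50% with r = 20% (0.50 + 0.50 × 0.20 = 0.60). It fits q = 60% with no new findings at all (0.60 + 0.40 × 0 = 0.60) equally well. The table cannot tell these apart. A new finding in a patient already counted also leaves no trace. Tabulating by finding type would reduce the problem, but not remove it where the same type of finding can exist before insertion.

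**The case against.** The strongest reply is that the plan has other baseline-referenced routes to a device injury.

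- **Adverse events.** An abnormal sign can be reported as an adverse event. SAP 12.1 defines treatment emergence against the pre-treatment state, and Protocol 7.3.3 plans summaries of events related to the device constituent and to the procedures. The exception in Protocol 9.1.1 covers disease signs collected as efficacy variables and judged unequivocally due to progression or lack of efficacy. It does not exempt device injury.
- **Lesions.** SAP 11.2 reports change from baseline in lesion number and has a worsened category for the video.
- **Layout.** SAP 4.0 places table specifications in a separate document that was not available for this review, and the visit tables are missing from the public copy. A by-visit layout may exist. Phase wording alone does not rule one out: SAP 12.5.2 uses similar wording for physical examination while referring to specific visits.

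Much of this stands. A reader might infer that device damage could not be detected in this trial; the documents do not support that. Exams before and after insertion are recorded, and a comparison can be derived.

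The objection does not show that the stated safety summary answers the safety question. The adverse event route depends on the investigator choosing to report a finding, whereas the protocol lists cystoscopic findings as a safety measure in their own right. Section 11.2 concerns lesions and bladder images as efficacy; it does not tabulate other abnormalities for safety. A possible layout in an unseen document does not replace a rule in the SAP.

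**Conclusion.** The point holds as a limited, inexpensive improvement. As written, SAP 12.5.3 yields a table that cannot distinguish new non-lesion cystoscopy findings from pre-existing ones, and comparison with placebo cannot make up for it. The size of the effect is not known: the documents give neither the prevalence of non-lesion findings at entry nor a rate of new ones. The figures above show only how the tally behaves, on the assumption that it counts any abnormality per patient.

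Four stronger readings are tempting and not supported.

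- **That the Treatment 1 row is 100% in every arm by eligibility.** This needs Hunner's lesions to count as safety abnormalities and the Day 0 exam to fall inside the phase. The documents state neither, and Protocol 6.5.8 treats confirming lesions as additional to the check for features that prevent safe use.
- **That lesion healing on LiRIS would hide device damage.** This needs lesions counted but Day 0 excluded, so it cannot hold together with the first reading. Nor can lesions be assumed to persist: Protocol 1.4 reports resolution at removal in 6 of 7 patients with lesions in an open-label study.
- **That a known between-arm difference is being diluted.** All arms carry the device, so there is no reason to expect device injury to differ between them.
- **That the SAP contradicts the protocol.** The protocol's safety measure names the occasions for recording findings and prescribes no before-and-after comparison.

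**What to change.** Replace the analysis sentence in SAP 12.5.3 with text to this effect:

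- The Day 0 exam before the first insertion is the baseline for cystoscopic findings and is not counted in Treatment 1.
- For each visit (Day 14 removal, Day 28 removal, Treatment 1 Week 4 Follow-up, exit without Treatment 2, Treatment 2 removal), by treatment group and finding type, give the number and percentage of patients with a finding absent at baseline, or recorded as worse where severity is recorded.
- For Treatment 2, the reference is the exam before the Treatment 2 insertion. Where that exam is also the Week 4 Follow-up exam, it serves both purposes.
- Hunner's lesions are kept separate from this table, since they are analysed in 11.2.

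No new exams are needed. The cost is one re-specified table and some coding to match finding types across exams. The supplied text shows no severity grading for non-lesion findings, so the worsened category applies only if the case report form records one; otherwise the table rests on findings absent at baseline.
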